## Change History record

CIP Change History		
Version	Summary of Changes	Author
1	Initial release	[name]

## A SYNOPSIS

### Title

FRailty WAlking Patterns (FRAP) Study

### Purpose

The aim of this study is to evaluate sit-stand phases and gait speed detection using an externally worn LINQ compared to an external reference (3D accelerometer, and/or the CAREN system) in one center in the Netherlands.

### Design

Prospective, non-randomized, single-center, post-market interventional study.

### Devices used in the study

The following products will be worn externally by the patients to capture movement signal:

- 3-D accelerometer – ActiGraph™ wGT3X-BT
- Accelerometer - Reveal LINQ™ with software RAMware REEF Research System, Rev 1.0 onboard
- DR220 Holter

All medical devices used in this study are CE marked. The intended use of the Reveal LINQ in this study will not be for medical purposes, but exclusively for technical reasons, therefore the Reveal LINQ will be considered a non-medical device in this study. The Reveal LINQ device will be used externally, will have the investigational software RAMware REEF Research System, Rev 1.0 onboard. The software will be downloaded through the 2090 programmer. Since RAMware REEF Research System is an accessory to the Reveal LINQ it will also be classified as a non-medical device. Subjects will perform part (i.e. Six Minute Walk Test, 4 Meter Gait Speed Test) of the walking exercises inside the Computer Assisted Rehabilitation Environment (CAREN) system, to record additional subject position information.

### Objectives and endpoints

#### Primary Objective

The primary objective of this study is to compare Gait parameters (i.e. gait speed, walking patterns) derived from the Reveal LINQ accelerometer signals during Six Minute Walk (6MW) Test, 4 Meter Gait Speed (4MGS) Test, Five Times Sit to Stand (FTSTS) Test, Expanded Timed Get-Up-and-Go (ETGUG) Test with those obtained from a validation accelerometer and the CAREN system.

#### Endpoints of the Study are the following:

- ETGUG phase data
- FTSTS timing
- Gait speed (4MGS test)
- Number of steps in 6 minutes (6MW test)
- Distance covered in 6 minutes (6MW test)
- Gait parameters from vertical acceleration axis

- Stand up phase slope
- HRV response to postural change

### Subject population

Approximately 20 Heart failure subjects will be enrolled in the study. This population was chosen to test the sensitivity of the accelerometer embedded in the LINQ device in a small cohort of subjects with reduced mobility and for which frailty is more prevalent than the general population, as well as recognized as an important prognostic indicator. Participants will be invited to attend one study visit. The study visit is expected to take approximately 2 hours. It is expected that the subjects will be enrolled over a period of 3 months and no follow up beyond the single visit is envisaged. The study will take place at a single center in the Netherlands (Maastricht University, Maastricht).

### Treatment

On arrival to the rehabilitation center subjects will have the Reveal LINQ, the 3D-accelerometers (one on the chest by medical-grade adhesives and a second at the level of the waist over the top of a medical grade adhesive) and the Holter attached externally. Then, they will be asked to perform the following exercises:

- Six Minute Walk (6MW) Test
- 4 Meter Gait Speed (4MGS) Test
- Five Times Sit to Stand (FTSTS)Test
- Expanded Timed Get-Up-and-Go (ETGUG) Test

Upon completion of the walking exercises, the Reveal LINQ device as well as the Holter and the Accelerometers will be removed from the subject and the subject's participation in the study will be complete. A Study Exit form will be completed.

### Inclusion criteria

- Chronic Heart Failure in NHYA class II and class III
- Willing to sign the informed consent form.
- At least 18 years of age.

### Exclusion criteria

- Not able to walk continuously for a period of 6 minutes and perform the walking exercises as necessary for the study protocol.
- Any known allergy to Titanium
- Any concomitant conditions which in the opinion of the investigator would not allow accurate measurement of gait and frailty parameters with an externally worn device.
- Any concomitant condition which in the opinion of the investigator would not allow a safe participation in the study.
- Enrolled in another study that could confound the results of this study, without documented pre-approval from a Medtronic study manager.

### Clinical Procedures

The point of enrollment is the time when a subject signs the Informed Consent Form. At that point, the subject is considered included in the study. All study data will be collected for each subject during Baseline visit and – should it be a standalone visit – during walking exercises performing visit. Information documented will include:

Study Procedure	Enrollment/Baseline	Walking Exercises Visit
Patient informed consent	x	
Inclusion/exclusion assessment	x	
Relevant Medical History	x	
Demographics	x	
Physical examination	x	
Medications	x	
REEF software upload/download		x
LINQ placement		x
Holter placement and Recording		x
Accelerometer placement and recording		x
ETGUG test		x
FTSTS test		x
6MW test		x
4MGS test		x
Exit subject	As they occur	
Study deviations	As they occur	

## B GENERAL INFORMATION

### B.1 Introduction

Frailty is a geriatric syndrome characterized by reduced homeostatic reserves, exposing the organism to extreme vulnerability to endogenous and exogenous stressors.

Frailty is prevalent in older people and involves a progressive physiological decline of multiple body systems, typical signs and symptoms include weight loss, fatigue, muscle weakness, slow or unsteady gait declines in activity.

Frailty is increasingly recognized as an important prognostic indicator in heart failure (HF) and is more prevalent in HF than the general population.

The identification of frailty in its early stage is important because interventions may potentially prevent, or delay the clinical consequences of frailty.

Of particular focus in this study will be walking speed as prior research has demonstrated that slow gait speed has the strongest prognostic ability of the traditional components used to assess frailty, and has been reported as one of the strongest to predict adverse outcomes, such as mobility disability, falls, or hospitalization.

Also of interest is the detection of posture changes as this may have implications for detecting changes in sleeping habits and could also provide context for other biomarker signals collected by the LINQ device.

The literature has been reviewed and the scientific soundness of the proposed analytical techniques evaluated. The rationale for this study design is to evaluate the feasibility of using the Reveal LINQ™ to monitoring walking patterns.

HF patients (the target population for the study in discussion) would make it possible to test the sensitivity of the accelerometer embedded in the LINQ device in a small cohort of subjects with reduced mobility and for which frailty is more prevalent than the general population, as well as recognized as an important prognostic indicator.

No risk to the subjects is expected with this study.

## B.2 Device information

No devices are implanted in this study. During the study visit subjects will be asked to wear the study device Reveal LINQ, with the REEF Investigational software installed, attached on the left hemitorax by medical-grade adhesives (i.e. Tegaderm, steri-strips).

Part of the walking exercises requested by the protocol will be performed within the Motek Medical CAREN (Computer Assisted Rehabilitation Environment) system. It is a hardware and software system for registration, evaluation and training of functional human behavior consisting of a motion base (with a dual belt instrumented treadmill), a camera real-time motion capture system, a projection screen and the D-flow software (<http://www.motekmedical.com/products/caren>).

Study Device:

- Reveal LINQ: A Medtronic, CE marked miniaturized insertable cardiac monitor (ICM) that is usually inserted subcutaneously through a minimally invasive procedure in patients with suspected arrhythmias for continuous monitoring of a patient's ECG and other physiological parameters.

In this study, the device will not be used according to its current indications. The Reveal LINQ will not be inserted subcutaneously, but will be worn externally on the chest and used as an accelerometer to register walking patterns. The same Reveal LINQ device will be worn externally by more than one subject and should be sanitized after each deployment as per common clinical practice.

Although the Reveal LINQ devices used in this study have engraved "Not for Human Use" as measure to prevent any accidental implantation, they are to be used in humans but not to be implanted. The parylene coating is removed due to the engraving. The Reveal LINQ package study specific labeling will be in English identifying the device as "Exclusively for Clinical Investigation - External use only". Furthermore, a medical-grade adhesive will be placed below the Reveal LINQ as an additional safety measure aiming to avoid direct contact with the titanium case of the Reveal LINQ and patient's skin. Since the purpose of this study is to investigate whether it is technically possible to obtain information about movement with the Reveal LINQ, the device will be considered a non-medical device.

- REEF Research System, Rev 1.0, Medtronic investigational RAMware uploaded on Reveal LINQ to activate the patient position sensor circuitry (the accelerometer). The RAMware REEF Research System is an accessory to the Reveal LINQ and will therefore also be classified as a non-medical device.
- 2090 Carelink Programmer: Medtronic. The Medtronic CareLink 2090 Programmer is a portable, line-powered (AC) microprocessor-based system. It contains investigational software (REEF User Interface Updates) to upload/download the REEF RAMware in the LINQ device. The investigational software is considered an accessory to the Reveal LINQ and will therefore also be classified as a non-medical device. The 2090 programmer containing the investigational software will be designated and labelled as "Exclusively for Clinical Investigation".

Monitoring equipment :

- Holter Monitor: CE marked. The North-East Monitoring DR220 Digital Recorder is a Holter monitor designed to facilitate ambulatory cardiac monitoring. The device is capable of storing real-time data to a SD memory card. For this study, this device is used to store the surface ECG and accelerometer signals from the Reveal LINQ™ during the walking exercises and will be used within the labeled Indications for Use.

- ActiGraph™ wGT3X-BT: ActiGraph Corporation, CE marked. This activity monitor contains a 3-D accelerometer and will be worn externally by the subjects during the walking assessment and will be used within the labeled Indications for Use.

The labeling of the CE marked devices will be according local language requirements.

### *B.2.1 Hospital equipment*

CAREN (Computer Assisted Rehabilitation Environment) System: Motek Medical. The CAREN System is a hardware and software system for registration, evaluation and training of functional human behavior. The CAREN system consists of a motion base (with a dual belt instrumented treadmill), a camera real-time motion capture system, a projection screen and the D-flow software.

## **B.3 Comparator information**

Not applicable.

# **C STUDY PLAN**

## **C.1 Study objectives**

The aim of this prospective, non-randomized, single-center, post-market interventional study is to evaluate sit-stand phases and gait speed detection in patients with chronic heart failure using an externally worn Reveal LINQ compared to an external reference (3D accelerometer, and/or the CAREN system).

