### *C.1.1 Primary objectives*

The primary objective of this study is to compare Gait parameters (i.e. gait speed, walking patterns) derived from the Reveal LINQ accelerometer signals during the Six Minute Walk (6MW) Test, 4 Meter Gait Speed (4MGS) Test, Five Times Sit to Stand (FTSTS) Test, Expanded Timed Get-Up-and-Go (ETGUG) Test with those obtained from a validation accelerometer and the CAREN system.

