## **C.2 Clinical endpoints**

The endpoints to be measured during the study are the following:

- ETGUG phase data
- FTSTS timing
- Gait speed (4MGS test)
- Number of steps in 6 minutes (6MW test)
- Distance covered in 6 minutes (6MW test)
- Gait parameters from vertical acceleration axis
- Stand up phase slope
- HRV response to postural change

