7.4. Handling of Missing, Unused, and Spurious Data and Dropouts

Missing data will not be imputed. The number included in each analysis will be reported so that the reader can assess the potential impact of missing data.

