7.9. Evaluation of Objectives

No formal statistical hypothesis will be tested.

The gait speed (and additional parameters) will be calculated from the Reveal LINQ accelerometer signals, from the validation accelerometer and/or from the computer assisted rehabilitation system. Correlation coefficients between the Reveal LINQ parameters and those from the reference system will be calculated for each maneuver (4MGS, FTSTS, ETGUG and 6MHW). The agreement between the Reveal LINQ derived parameters and the reference parameters will be reported and visualized using

Bland and Altman plots. The agreement between the parameters derived during the different maneuvers will also be evaluated using correlation coefficients and Bland-Altman plots.

Additional exploratory analyses of the data will be conducted as deemed appropriate.

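### The stated aim includes detecting sit-stand phases, but no planned analysis directly quantifies missed or false sit-stand transitions

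*Protocol*

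**What the plan says.** The aim in Protocol C.1 is "to evaluate sit-stand phases and gait speed detection in patients with chronic heart failure", with the 3D accelerometer and/or CAREN as reference. The Synopsis and SAP section 3 repeat it in substance. The formal primary objective in Protocol C.1.1 and SAP section 4 is worded differently: "The primary objective of this study is to compare Gait parameters (i.e. gait speed, walking patterns) derived from the Reveal LINQ accelerometer signals", set against a validation accelerometer and CAREN across all four tests. The background in Protocol B.1 adds "Also of interest is the detection of posture changes".

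The sit-stand endpoints in Protocol C.2 are "ETGUG phase data", FTSTS timing, stand-up phase slope and the HRV response to a change of posture. None is a number of transitions detected, missed or falsely reported. The only count in the list is steps in the six-minute walk (6MW).

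For the objective, SAP 7.9 says "Correlation coefficients between the Reveal LINQ parameters and those from the reference system will be calculated for each maneuver" and adds Bland-Altman plots. Protocol H.1 says the same. Both documents allow exploratory analyses without specifying any. On missing values, SAP 7.4 says "Missing data will not be imputed" and undertakes to report the number in each analysis. SAP 7.1.3 limits the Analysis Population to subjects with good-quality Holter, LINQ, Actigraph and CAREN recordings but gives no quality criterion. The definition in Protocol H.1 has no such condition.

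**The concern.** For a feasibility study, how often extraction fails is a main result. Correlation and Bland-Altman limits are computed on pairs, and a transition that LINQ does not find has no LINQ time or slope and forms no pair. The agreement figures are therefore conditional on success. A device that times well the stand-ups it finds, but overlooks a material share of them, could look as good as one that finds them all. A quality filter with no stated criterion adds to this, because a recording from which nothing could be extracted might be judged poor and excluded before any result is produced.

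**Working it through.** **Plan's own figure.** There is none to reproduce. The sample size of about 20 is stated without a calculation, and neither document gives a detection rate or target precision.

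**Step 1: follow a failure through the planned outputs.**
- *FTSTS timing.* Protocol F.3 defines one time per test. A missed repetition could make the LINQ total wrong (a Bland-Altman outlier) or unavailable (a lower n). If the algorithm ran from the first to the last detected stand-up, a missed middle repetition would leave the total unchanged. The documents do not give the algorithm.
- *ETGUG phase data.* A missed stand-up or sit-down removes a phase boundary, so the value is probably absent and n falls.
- *Stand-up phase slope.* A missed event has no slope. The documents do not say whether slope is analysed per event or per subject. If it is averaged within subject, the loss does not show.
- *False transitions.* They do not lower n. They may go unpaired or may distort a total.

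Some failures therefore leave a trace, but no output counts them or labels them as detection failures.

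**Step 2: events available.** Protocol F.3 fixes 5 stand-ups in FTSTS and 1 in ETGUG. With 20 subjects, 20 x 5 = 100 and 20 x 1 = 20, giving 120 stand-ups. Sit-downs are additional and are not in the figures below.

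**Step 3: precision of a detection rate.** The 90% rate (108 of 120) and the within-subject correlations (ICC) are assumptions.
- Independent events: the exact (Clopper-Pearson) 95% interval for 108/120 is 83.2% to 94.7%.
- Clustered events: design effect = 1 + (6 - 1) x ICC. At ICC 0.3 this is 1 + 5 x 0.3 = 2.5, so effective n = 120 / 2.5 = 48. The Wilson 95% interval at 90% is 78.3% to 95.7%.
- Over a range of ICC, using the simple half-width 1.96 x sqrt(0.9 x 0.1 / effective n):

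| ICC | Design effect | Effective n | Half-width (points) |
|---|---|---|---|
| 0 | 1.0 | 120 | 5.4 |
| 0.1 | 1.5 | 80 | 6.6 |
| 0.3 | 2.5 | 48 | 8.5 |
| 0.5 | 3.5 | 34.3 | 10.0 |
| 1 | 6.0 | 20 | 13.1 |

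The planned sample gives a usable descriptive estimate.

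**Step 4: does per-event agreement respond to misses?** A simulation of 3000 runs took 20 subjects x 5 stand-ups and analysed detected pairs only. It assumed SDs of 0.5 s between subjects, 0.2 s within subjects and 0.1 s for device error, with misses at random.

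| Missed | Mean pairs | Mean r | Limits-of-agreement half-width |
|---|---|---|---|
| 0% | 100 | 0.981 | 0.195 s |
| 10% | 90 | 0.981 | 0.195 s |
| 20% | 80 | 0.981 | 0.195 s |
| 40% | 60 | 0.981 | 0.195 s |

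Bias was about zero throughout. At 40% missed, a subject loses all five pairs with probability 0.4^5 = 0.010, so about 20 x 0.990 = 19.8 subjects still contribute. An n counted in subjects would barely move. This applies to endpoints analysed per event. It does not describe the FTSTS total, which is one value per test.

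**The case against.** The strongest reply is that the formal primary objective and primary endpoint are a comparison of gait parameters, for which correlation and Bland-Altman are usual tools. The listed sit-stand endpoints are timing, phase data and slope, and agreement methods suit those too. The study tests no hypothesis, enrols about 20 subjects and leaves room for exploratory work. All of this stands. It limits the point to the sit-stand part of the aim, but it does not supply the missing output, since unspecified exploratory analyses commit to nothing.

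A reader might infer more than the documents support:
- *That detection failures never reach any result.* SAP 7.4 promises the number in each analysis, and a miss can surface there or as an outlying FTSTS total. The unit of that number is not stated, however, and false detections do not reduce it.
- *That the plan cannot answer its aim.* The aim also covers gait speed, a continuous quantity that the planned methods address.
- *That choosing this population "to test the sensitivity of the accelerometer embedded in the LINQ device" promises a true-positive rate.* The phrase can equally mean how well the sensor responds to weak movement, so nothing here rests on it.
- *That correlation would fail on stand-up counts because the test fixes them.* No such correlation is planned.

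**Conclusion.** The point holds in limited form. The stated aim includes detection of sit-stand phases, and no planned analysis directly quantifies missed or false transitions. Failures would appear at most indirectly, and the undefined quality condition could hide some of them. This is a reporting gap that should be closed in the SAP. It is not a flaw in the design or in the methods chosen for the primary objective.

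The 120 stand-ups follow from the protocol's test definitions at 20 subjects with complete tests. The 90% detection rate, the ICC and the simulation SDs are illustrative and come from neither document. The intervals of about 83% to 95% and about 78% to 96% cover stand-ups only and use two different interval methods. The simulation also assumes random misses. If slow or weak stand-ups were missed more often, agreement on the rest could differ from what it shows.

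**What to change.** Add to SAP 7.9, for FTSTS and ETGUG:

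> A detected transition (sit-to-stand or stand-to-sit) will be defined before analysis, with a time-matching rule against transition times derived from the ActiGraph signal and against the transition sequence fixed by the test. Detected, missed and false transitions will be reported per subject and per test, with sensitivity and subject-clustered 95% confidence intervals. Undetected transitions count as failures. Agreement in timing, phase and slope will be reported for detected transitions with that denominator stated. The number of recordings excluded for quality, and the criterion used, will be reported.

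Three details need settling:
- **Reference.** CAREN is stated only for 6MW and the 4 Meter Gait Speed test. For FTSTS and ETGUG the named sources are the ActiGraph and the CRF test records, and the protocol does not say that the CRF holds transition-level times. Subjects wear one accelerometer on the chest and one at the waist, so the SAP should say which is used.
- **Alignment.** The simultaneous tap on LINQ and Actigraph in Protocol F.3 gives a common marker for the matching rule.
- **Sit-downs in FTSTS.** Five stand-ups imply at least four sit-downs between them. The protocol does not say whether a final one belongs to the test, so the expected sequence should be fixed.

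The cost is modest offline work to derive event times from the ActiGraph signal, plus one table. It needs no extra subjects, visits or recordings. ActiGraph-derived times can themselves be wrong, which is why the fixed sequence is used alongside them.

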### *C.1.1 Primary objectives*

The primary objective of this study is to compare Gait parameters (i.e. gait speed, walking patterns) derived from the Reveal LINQ accelerometer signals during the Six Minute Walk (6MW) Test, 4 Meter Gait Speed (4MGS) Test, Five Times Sit to Stand (FTSTS) Test, Expanded Timed Get-Up-and-Go (ETGUG) Test with those obtained from a validation accelerometer and the CAREN system.

## **C.2 Clinical endpoints**

The endpoints to be measured during the study are the following:

- ETGUG phase data
- FTSTS timing
- Gait speed (4MGS test)
- Number of steps in 6 minutes (6MW test)
- Distance covered in 6 minutes (6MW test)
- Gait parameters from vertical acceleration axis
- Stand up phase slope
- HRV response to postural change

### **C.3 Study hypothesis**

As this is a feasibility study, no formal statistical hypotheses are being tested. The Study regards the feasibility of extracting walking patterns from the accelerometer embedded in the Reveal LINQ.

